### **7.2 Analysis**

The statistical analysis will be carried out upon the data collection through SPSS 20.0. software. The categorical variables will be described in terms of proportion, while the continuous variables in terms of average and standard deviation or median and interquartile range. The normal intake of the demographic variables and of the outcome measures will follow through the Kolmogorov-Smirnov. The possible post intervention inter-group and intra-group differences relative to the continuous outcome measures will be evaluated through the ANOVA test for repeated measurements and an eventual post hoc analysis will be carried out later. The threshold value of the level of significance will be set at 0.05.

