### **Outcomes**

The primary outcome will be the evaluation of the disability through a Oswestry Disability Index questionnaire. The secondary outcomes will be the rating of the pain (Numeric Rating Scale), the quality of life (Short-Form 36) and the fear of movement (Tampa Scale of Kinesiophobia). The outcome measures will be taken before the treatment (T0), after three weeks (T1) and four months upon the end of the treatment (T2). At T0 the subjects' attention skill will be evaluated.

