**Statistical methods and data analysis**

Upon data collection the normality and homogeneity of the demographic variables and of the outcome measures to the baseline will be evaluated. Possible differences after treatment, inter-group, intragroup will be investigated through ANOVA test for repeated measurements including any possible post hoc analysis.

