## **4 Study outcomes**

### **4.1 General outcomes**

The outcome of the study is to determine the efficacy of the Action Observation Training in the treatment of chronical LBP affected patients.

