### **4.2 End-points**

#### ***4.2.1 Primary Endpoint***

The primary outcome will be to evaluate the disability through the Oswestry Disability Index (ODI-I). This is a specific pathology questionnaire, it is self-administered and validated in Italian [11]. It is made of ten items about everyday activities. The scores will be interpreted as described by

Fairbank [12]: 0-20% is considered minimum disability, 21-40% modest disability, 41-60% severe disability, 61-80% serious disability and 81-100% total disability [13].

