## **7 Statistical considerations**

### **7.1 Sample size**

The Oswestry Disability Index represents the primary outcome measure. The sample size has been calculated considering an MCID of 12.8 points among the general population with a 14 point standard deviation. Assuming a 80% power and a probability to refuse the null hypothesis when true (alpha error) of 5%, 25 patients per group will be recruited.

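### The plan makes ODI primary at a single 5% level but does not name the between-group ODI result that decides, the trigger for post hoc tests, or the descriptive status of intra-group change

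*Combined protocol and SAP*

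**What the plan says.** Section 4.1 gives the aim: "The outcome of the study is to determine the efficacy of the Action Observation Training" in chronic low back pain. Section 4.2.1 makes the ODI primary. It describes the questionnaire and its severity bands, but gives no visit and no contrast. ODI is measured before treatment (T0), three weeks after the start (T1) and four months after the end of treatment (T2), according to the Synopsis (Outcomes) and Section 6.1.

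Section 7.1 sizes the trial on an ODI difference of 12.8 points with SD 14, 80% power and "a probability to refuse the null hypothesis when true (alpha error) of 5" per cent, giving 25 per group. The difference is not tied to a visit.

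Section 7.2 states that "inter-group and intra-group differences relative to the continuous outcome measures will be evaluated through the ANOVA test for repeated measurements", and then that "an eventual post hoc analysis will be carried out later". It adds: "The threshold value of the level of significance will be set at 0.05". The Synopsis (Statistical methods and data analysis) says much the same: "Possible differences after treatment, inter-group, intragroup will be investigated through ANOVA test for repeated measurements including any possible post hoc analysis". Neither place names an interaction, a trigger for post hoc tests, a list of contrasts, an adjustment for multiple tests, or an order between inter-group and intra-group results.

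**The concern.** A two-group, three-visit repeated-measures ANOVA does not give one answer on treatment. It gives a group main effect and a group-by-time interaction, and post hoc work adds a group difference at T1 and another at T2. All four are inter-group results. The trial is sized for one test at 5%, but the plan does not say which of the four is that test.

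Two things are at stake. First, if more than one of these results can support the claim, the false-positive risk is above 5%, and a mixed result (T1 significant, T2 not) has no pre-set reading. Second, the four results do not have the same power, so a choice made after the data are seen could decide whether the trial is called positive.

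A smaller gap concerns intra-group differences, which are listed beside inter-group ones at the same threshold. Under Section 6.1 both arms do the same exercises; only the video or the brochure differs. A change within the AOT arm therefore mixes the effect of exercise, the passage of time and any effect of AOT, and cannot isolate the last.

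**Working it through.** **Inputs.** From Section 7.1: difference 12.8, SD 14, alpha 5%, 25 per group. From Section 6.1: visits T0, T1 and T2. Assumed, because the documents do not give them: two-sided tests, normal data, equal correlation ρ between visits of 0.3-0.8 for error and 0.3-0.7 for power, and no dropout unless stated.

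**The plan's own figure.** For a two-sample t-test with d = 12.8/14 = 0.914, 80% power at two-sided 5% needs 20 per group (19 by the normal approximation). With 25 per group the power is 88.6%. The stated 25 is therefore not reproduced from the stated inputs. It would follow from 20/0.8 = 25, a 20% dropout allowance that is not stated. The mismatch is on the safe side, and this point does not rest on it.

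**False-positive risk for ODI when AOT has no effect.** Two independent tests at 5% give 1 − 0.95² = 9.75%. Simulated, with 25 per arm:

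| What counts as success | ρ = 0.3 | 0.5 | 0.7 | 0.8 |
|---|---|---|---|---|
| Unadjusted difference at T1 or at T2 | 9.7% | 9.3% | 8.6% | 7.9% |
| Baseline-adjusted difference at T1 or at T2 | 9.8% | 9.7% | 9.5% | 9.2% |
| Interaction alone | 5.1% | 4.8% | 5.2% | 4.9% |
| Interaction first, then unadjusted T1 or T2 | 2.2% | 1.5% | 1.2% | 0.9% |
| Interaction first, then adjusted T1 or T2 | 3.2% | 3.2% | 3.7% | 3.7% |

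If either the group main effect or the interaction counts, the rate is 9.5-10.0%. If the visit contrasts after the gate are changes from T0, the gated rate is 4.0-4.2% (ρ 0.3-0.7).

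**Power for a 12.8-point benefit at both T1 and T2, 25 per arm.**

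- *Baseline-adjusted difference at one named visit.* The residual SD is 14√(1 − ρ²), which is 13.4, 12.1 and 10.0 at ρ = 0.3, 0.5 and 0.7. Simulated power at T1 is 90.4%, 94.9% and 99.3%; T2 is within half a percentage point of these.
- *Group-by-time interaction.* The group differences over T0, T1 and T2 are 0, 12.8 and 12.8, with mean 8.53. Their squared deviations sum to 109.2. The noncentrality is (25/2) × 109.2 / (196 × (1 − ρ)), which is about 9.9 at ρ = 0.3 and 23.2 at ρ = 0.7, on 2 and 96 degrees of freedom. Simulated power is 79.9%, 92.0% and 99.2%.
- *Group main effect.* This averages T0 in with T1 and T2. Randomisation makes the expected T0 difference zero, so the 12.8 is diluted to 12.8 × 2/3 = 8.53. The SD of a patient's three-visit mean is 14√((1 + 2ρ)/3), which is 10.2, 11.4 and 12.5. The noncentrality 8.53/(SD × √(2/25)) is 2.95, 2.64 and 2.41, giving power of about 82%, 73% and 66%. It falls as the correlation rises, while the power of the other two tests rises.

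**If the benefit is not constant** (assumed cases, ρ 0.3-0.7). For 12.8 at T1 fading to 6.4 at T2: adjusted T1 90-99%, adjusted T2 38-59%, interaction 67-97%. For 6.4 at T1 rising to 12.8 at T2: adjusted T1 37-59%, adjusted T2 91-99%, interaction 67-96%.

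**If 20 per arm complete** (assumed; Section 8 excludes incomplete acquisitions). For a constant 12.8: adjusted T1 83-97%, interaction 70-97%.

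**The case against.** **The wording implies ANOVA first.** This is the strongest objection, and much of it stands. An eventual post hoc analysis reads most naturally as a conditional step after the ANOVA. If the interaction is the gate, the error is about 1-4%. A reader might infer from the 8-10% figure that the plan commits to an inflated error rate. The documents do not support that, because the figure applies only if more than one result may count. The objection does not close the gap, however. No condition is written, and ANOVA first does not say which ANOVA effect opens the gate. The most literal inter-group effect is the group main effect, and accepting either it or the interaction brings the risk back to about 10%.

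**Intra-group may only describe the within-subject factor.** This also stands in part. A reader might infer that the plan will run separate before-and-after tests in each arm and claim efficacy from the AOT arm alone. No section names such tests or such a claim, and the efficacy aim and the randomised controlled design (Section 6) point to the between-group comparison. What remains is a labelling gap: nothing says these results are descriptive.

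**Baseline adjustment is a preference.** The missing decision rule can be repaired within the planned ANOVA, so replacing that method is not required. The adjusted test is preferred because it uses T0 data already collected and has at least as much power when the benefit is constant. With a benefit that changes between visits, it loses to the interaction if the weaker visit was chosen.

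**Conclusion.** The point holds as a missing decision rule, not as a demonstrated error in a committed analysis. ODI is primary at one 5% level, and four between-group ODI results remain open. Depending on the unstated rule, the false-positive risk lies between about 1% and 10%. For a benefit of 12.8 points at both visits, power lies between about 66% and 99%.

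These figures assume 25 completers per arm, SD 14, normal data and equal visit correlations in the ranges given. Other correlations would move the numbers, but the absence of a named deciding result is plain from the text and depends on none of them. The intra-group part is minor and follows from the design alone. The sponsor should correct this before the data are seen.

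**What to change.** In Sections 4.2.1 and 7.2, name one decisive between-group ODI test at two-sided 0.05.

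- **Preferred:** the group difference at one pre-chosen visit, adjusted for T0 ODI. Test the other visit only if the first is significant. The documents do not rank T1 and T2, so the sponsor should choose the visit at which benefit is to be claimed and give the reason.
- **If the planned ANOVA stays primary:** name the group-by-time interaction, not the group main effect, as the gate, with a sphericity correction. Under one unequal correlation pattern (0.8/0.3/0.3) the uncorrected interaction test rejected in about 6% of null trials. State whether the T1 and T2 contrasts use levels, changes or adjusted values, and how a mixed T1/T2 result will be read.
- **In either case:** state that intra-group changes are descriptive and cannot support an efficacy claim.

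The cost is a few sentences, with no new visits or data. The preferred option replaces the planned ANOVA for the primary result; the second keeps it. Under the preferred option there is no confirmatory claim at the second visit if the first fails, and power is lower if the benefit is smaller at the chosen visit. If T2 or the interaction is chosen, Section 7.1 should be rechecked for a fading benefit and for dropout.

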### **6.1 General design**

The patients will be recruited and then randomly assigned by an external collaborator (allocation concealment) to the experimental group or to a control group. The patients belonging to the experimental group will be asked to watch a video showing a person carrying out some exercises (12 exercises: 3 stretching exercises, 3 core stability exercises, 3 mobilization exercises and 3 functional exercises) and later on they will be asked to repeat them. The observation of the exercise and its performance will last 8 minutes (4 minutes for observation and 4 minutes to repeat them). On the other hand, the patients belonging to the control group will be given a brochure with the same exercises the patients of the experimental group received through the video. They will be asked to read the exercise 3 times and to carry it out for 4 minutes. Both groups will have to watch the video or read the brochure and repeat the exercises 5 times per week for 3 weeks. They will be

provided with a diary to write daily notes about the performance of the exercises (day and time of the performance, possible problems, etc).

The patients will be evaluated before the treatment (T0), three weeks upon its beginning (T1) and 4 months upon the end of it (T2). The evaluation will consist in the administration of the Oswestry Disability Index, of the Tampa Scale of Kinesiophobia, of the Numerical Rating Scale and of the Medical Outcomes Study Short Form 36. At T0 the subjects' attention skill will be evaluated through the Brief Cognitive Assessment Tool [16]

A physiotherapist will instruct the patients about the exercises to repeat while a second blinded physiotherapist about the group the patients belong to, will administer the evaluation scales.

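### The planned repeated-measures ANOVA names no baseline covariate; adjusting for T0 ODI would estimate the primary effect more precisely at almost no cost

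*Combined protocol and SAP*

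**What the plan says.** The primary outcome is the ODI (section 7.1), collected at T0, T1 and T2 (section 6.1). Section 7.2 states that differences between and within groups on the continuous outcomes "will be evaluated through the ANOVA test for repeated measurements and an eventual post hoc analysis will be carried out later". The synopsis says the same: "Possible differences after treatment, inter-group, intragroup will be investigated through ANOVA test for repeated measurements including any possible post hoc analysis". Neither place names a covariate, a model term, a contrast or a primary visit.

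The synopsis also plans to check normality and homogeneity of the outcome measures at baseline, but attaches no consequence to that check. No other use of the T0 ODI is described. The sample size in section 7.1 was set "considering an MCID of 12.8 points among the general population with a 14 point standard deviation", at 80% power and 5% alpha, giving 25 per group. It does not say whether 14 is the SD of the score or of the change, and it gives no correlation between visits.

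**The concern.** T0 ODI will be available for every patient and is likely to predict later ODI. A repeated-measures ANOVA with T0 as a level can be read in two ways, and neither makes the best use of it.

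- **Group-by-time interaction.** This is a change-type comparison. It subtracts the whole of any chance T0 difference between arms, whereas regression on baseline subtracts only the fraction r, the baseline-to-follow-up correlation. The change contrast therefore over-corrects by (1 − r) times the imbalance, and its variance is larger.
- **Group main effect.** T0, where no treatment effect can exist, is averaged in with T1 and T2. A sustained effect of 12.8 points is diluted to two-thirds, about 8.5 points.

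At stake are the width of the confidence interval for the primary effect and how far a chance baseline difference moves the estimate. Validity is not at stake.

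**Working it through.** **Inputs from section 7.1:** difference δ = 12.8, SD σ = 14, power 80%, alpha 5%, n = 25 per group. **Assumptions not in the documents:** two-sided test; 14 is the SD of the score; equal correlation r between all visits (compound symmetry), with r = 0.3, 0.5 and 0.7 as the main range and 0.9 as an extreme.

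**The plan's own figure.** n = 2 × 14² × (1.96 + 0.842)² / 12.8² = 18.8, so 19 per group (20 with the t distribution). The stated 25 gives 89% power for a comparison of follow-up scores alone. So 25 is more than these inputs require. That is a separate matter, and this point does not depend on it.

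**Variance of the group effect**, in units of σ²(2/n):

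- One visit, change from T0: 2(1 − r).
- One visit, ANCOVA on T0: (1 − r²), times 1 + 1/(2n − 4) = 1 + 1/46 = 1.022 for estimating the slope.
- Mean of T1 and T2 minus T0: 1.5(1 − r).
- Mean of T1 and T2, ANCOVA on T0: (1 + r)/2 − r², times 1.022.

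Before the slope cost, the variance ratio of ANCOVA to change is (1 + r)/2 for one visit and (1 + 2r)/3 for the mean. With the cost, the single-visit ratio stays below 1 while r < 2/1.022 − 1, about 0.96.

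**Half-width of the 95% CI** = t × √(variance × 14² × 2/25), with 48 df for change and 47 for ANCOVA. Example at r = 0.5, one visit: the change SD is 14 × √1 = 14.0, the SE is 3.96 and the half-width 7.96. The ANCOVA SD is 14 × √(0.75 × 1.022) = 12.26, the SE is 3.47 and the half-width 6.97.

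| r | Ratio before slope cost, one visit | Half-width, one visit: change / ANCOVA | Half-width, mean of T1 and T2: change / ANCOVA | Power for 12.8 at one visit: change / ANCOVA |
|---|---|---|---|---|
| 0.3 | 0.65 | 9.4 / 7.7 | 8.2 / 6.0 | 76% / 91% |
| 0.5 | 0.75 | 8.0 / 7.0 | 6.9 / 5.7 | 89% / 95% |
| 0.7 | 0.85 | 6.2 / 5.8 | 5.3 / 4.8 | 98% / 99% |
| 0.9 | 0.95 | 3.56 / 3.51 | 3.08 / 3.01 | both about 100% |

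**Simulation.** With 4,000 trials per setting and a true effect of 8 points, the SD of the estimate (change against ANCOVA) was 4.71 / 3.86, 3.86 / 3.46 and 3.08 / 2.86 at r = 0.3, 0.5 and 0.7. Type I error was 4.4% to 5.1% for every method, so the planned test is valid.

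**The planned 2-df interaction test.** For an effect sustained at T1 and T2, the noncentrality is nδ²/[3σ²(1 − r)], with F on 2 and 4n − 4 = 96 df. At r = 0.3 this is 25 × 163.84 / (3 × 196 × 0.7) = 9.95, which gives 80% power. At r = 0.5 and 0.7 power is 92% and 99%. Power drops below 80% only under further assumptions. With r = 0.3 it is 70% if 20 per arm are evaluable, and 67% if half the effect remains at T2. With r = 0.2 the noncentrality is 8.71 and power is 74%.

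**Group main effect including T0.** The difference is (2/3) × 12.8 = 8.53 and the variance σ²(1 + 2r)/3. Power is 82%, 73% and 66% at r = 0.3, 0.5 and 0.7.

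**Chance imbalance at T0.** The SE is 14 × √(2/25) = 3.96 points, so a difference of more than 4 points in either direction occurs in about 31% of trials. A 4-point imbalance shifts the change estimate relative to ANCOVA by 4(1 − r) = 2.8, 2.0 and 1.2 points at r = 0.3, 0.5 and 0.7.

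**The case against.** The strongest reply is that nothing here is broken. Repeated-measures ANOVA over three visits is a recognised analysis, it holds its type I error, and the interaction test keeps 80% power or more at 25 per arm for a sustained effect with r of 0.3 or above. This stands, and it limits the point to efficiency.

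Several narrower objections also have weight.

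- **SD of score or of change.** If 14 is the SD of change, single-visit change power is 89% at every r and the interaction has 92% (84% with 20 evaluable per arm, 82% with half the effect at T2). The figures below 80% for those two tests then disappear, and the imbalance SE becomes 3.4 at r = 0.3 and 5.1 at r = 0.7. The variance ratio between ANCOVA and change does not alter.
- **Unknown correlation.** At r = 0.8 the single-visit half-widths are 5.04 against 4.83, and at 0.9 they are 3.56 against 3.51. The direction holds, but the gain becomes trivial.
- **T0 as a level is inferred.** If the between-group test used only T1 and T2, change from T0 would be the wrong comparator. Adjustment still helps: for the mean of T1 and T2 the half-width falls from 6.4 to 6.0 at r = 0.3 and from 6.9 to 5.7 at r = 0.5.
- **A separate gap.** The absence of a named primary visit or contrast is not itself a missing covariate. Adjustment does not rescue a fading effect: with half the effect left at T2 and T2 tested, power at r = 0.3, 0.5 and 0.7 is 27%, 35% and 53% for change, and about 38%, 44% and 59% for ANCOVA.
- **Choice of model.** Keeping T0 as an outcome with the group means constrained equal at T0 gives essentially the same precision, so ANCOVA is not the only remedy.

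**Conclusion.** The point holds as a recommended improvement, not as an error. No baseline adjustment is planned although T0 ODI is already collected, and adjusting for it gives a more precise effect estimate than a change-type contrast for any r below about 0.96 at this sample size. After the slope cost, the single-visit variance falls by about 34%, 23% and 13% at r = 0.3, 0.5 and 0.7, and by 3% at r = 0.9.

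The direction does not depend on which SD the 14 points represent. The absolute half-widths, powers and imbalance figures do, and they also rest on compound symmetry and an assumed r. Confidence is moderate, because the documents do not give r and do not say how T0 enters the ANOVA. The stated 80% power is not shown to fail.

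**What to change.** In section 7.2 and the synopsis, make the primary ODI analysis a baseline-adjusted model of T1 and T2: fixed effects for group, visit, group-by-visit, baseline ODI and baseline-by-visit, with unstructured covariance. SPSS, the software already named, fits this with MIXED. If a single visit is analysed, use ANCOVA of ODI on group and T0 ODI. A repeated-measures model with T0 means constrained equal across groups is an acceptable alternative.

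Name the primary visit or contrast (T1, T2 or their mean) before any outcome data are seen, because power depends on it if the effect fades. Report the adjusted between-group difference with its 95% CI, and use the same form for NRS, TSK and SF-36.

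The cost is SAP wording and that one decision, with no new data, visits or patients. Single-visit ANCOVA spends one degree of freedom and about 2% of variance at 25 per arm; the two-visit model estimates a second baseline slope.

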## **8 Study abandonment**

The patients who during or at the end of each scheduled evaluations set by the protocol will abandon the study will be immediately excluded from it. The patients will be informed about the possibility to quit the study also during the follow-up periods, after informing any experimenter. The acquisitions which have not been completed by the patients will be excluded from the analysis of the results.

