### **10.3 Informed consent**

All subjects will receive information regarding the study, the performance and the relevant outcome of the study. They will also be informed about the strict confidentiality their data will be treated. It is underlined that the participation is voluntary and that the subject will be allowed to quit the study at any time. The informed consent will be filled by each subject and only when it has been collected the relevant data will be entered in the collection sheet (*Enclosure E*).

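### Section 8 leaves the fate of leavers' earlier data open; with repeated-measures ANOVA the plan most likely compares completers only, which is biased if loss relates to outcome and differs by arm

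*Combined protocol and SAP*

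**What the plan says.** Section 8 says that patients who leave during or at the end of a scheduled evaluation "will abandon the study will be immediately excluded from it". It then says: "The acquisitions which have not been completed by the patients will be excluded from the analysis of the results". The word *acquisition* is not defined; it could mean a questionnaire, a visit or a patient's whole series.

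Section 7.2 says that differences between and within groups in the continuous outcomes "will be evaluated through the ANOVA test for repeated measurements", in SPSS 20.0. The synopsis names the same test and adds nothing on missing values.

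Leaving is foreseen. Section 8 says "The patients will be informed about the possibility to quit the study also during the follow-up periods", and Section 10.3 says that "the participation is voluntary and that the subject will be allowed to quit the study at any time". Section 6.1 places T1 three weeks after the start and T2 four months after treatment ends.

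The text available does not define an analysis set, name a missing-data method, plan a sensitivity analysis, give an expected loss rate, or say whether completed T0 and T1 assessments of a leaver stay in the analysis.

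**The concern.** Randomisation protects the comparison of everyone randomised. It does not protect a comparison of those who stayed. If staying depends on how the patient is doing, and that dependence differs between arms, the completers in the two arms are no longer comparable, and the ODI difference mixes the effect of the video with the effect of selection.

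The mildest reading of Section 8, dropping only the unfinished assessment, does not avoid this. Classical repeated-measures ANOVA over T0, T1 and T2 needs all three values from each patient, so a completed T1 is lost whenever T2 is missing. Leaving the rule open also allows the analysis population to be chosen after the data are seen.

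**Working it through.** **1. The plan's own figure.** There is no loss figure to reproduce; the nearest is the 25 per group in Section 7.1. With a difference of 12.8, SD 14, 80% power and 5% alpha (two-sided assumed, sidedness not stated), n = 2 × [(1.96 + 0.842) × 14 / 12.8]² = 18.8, so 19 per group, or 20 by the t-test. The stated inputs therefore do not give 25. By the noncentral t, power is 89% with 25 per arm and 80% with 20 (a two-sample approximation, not the group-by-time test). The spare five per arm cover loss of precision up to 20% (20 / 0.8 = 25). They do nothing for bias.

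**2. Assumptions for the bias.** From the plan: SD 14, 25 per arm. Assumed: no true effect; correlations T0-T1 0.5, T0-T2 0.4, T1-T2 0.7; all loss after T1; log-odds of leaving change by 1 to 1.5 per SD of whatever drives loss.

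**3. Bias with 30% loss in one arm and 10% in the other.** Two drivers are compared: change from T0 to T1, and the T1 score. Both have SD 14, because the SD of change is 14 × √[2 × (1 − 0.5)] = 14. Simulation gives the same gap δ between arms in the completers' mean of the driver in both cases: 2.3 to 2.9 points. The other visits shift by their regression on the driver. For T1 change: T0 by (0.5 − 1) = −0.5δ, T1 by (1 − 0.5) = 0.5δ, T2 by (0.7 − 0.4) = 0.3δ. For the T1 score: T0 by 0.5δ, T1 by δ, T2 by 0.7δ. Absolute bias in ODI points:

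| Completers-only contrast | Loss driven by T1 change | Loss driven by T1 score |
|---|---|---|
| Change at T1 | (0.5 + 0.5)δ = 2.3 to 2.9 | (1 − 0.5)δ = 1.15 to 1.45 |
| Change at T2 | (0.3 + 0.5)δ = 1.84 to 2.32 | (0.7 − 0.5)δ = 0.46 to 0.58 |
| Raw score at T1 | 0.5δ = 1.15 to 1.45 | δ = 2.3 to 2.9 |
| Raw score at T2 | 0.3δ = 0.69 to 0.87 | 0.7δ = 1.61 to 2.03 |
| Group-by-time false positives, uncorrected | 8.3% to 9.2% | about 6% |

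With no loss the uncorrected false-positive rate is 5% to 6%. With the Greenhouse-Geisser correction, the change-driven figures are 7.1% to 8.3% against 5.0%.

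**4. Other patterns, T1-change-driven.**
- Equal 20% loss in the same direction: bias about 0, false positives 5.1% to 5.6%.
- 25% v 15%: bias 1.2 to 1.5 at T1 and 0.9 to 1.1 at T2, false positives 6.0% to 6.7%, hardly above the reference.
- Equal 20% in opposite directions by arm: bias 4.8 to 6.3 and 3.9 to 5.1, false positives 17.5% to 28.5%. If the T1 score drives the same pattern, T2 change bias is 1.0 to 1.3 and false positives are about 7% to 10%.

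**5. What using all available values achieves.** A likelihood estimate from all T0, T1 and T2 values returns to about 0 in every scenario above. If the unseen T2 change drives loss, it does not. With 30% v 10%, completers-only bias at T2 is 2.46 to 3.14 and the likelihood estimate still carries 1.09 to 1.47, that is 1.09 / 2.46 = 44% to 1.47 / 3.14 = 47%.

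**The case against.** *Completers-only is not stated.* Correct. Section 8 excludes leavers from the study, not explicitly their earlier data from the analysis, and a post hoc T0-T1 comparison could keep patients who miss T2. A reader might infer that the plan orders deletion of leavers' data; the text does not support that. What stands is that the main named test cannot use an incomplete series.

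*Other documents may cover it.* The consent and privacy enclosures (D and E) are not among the documents reviewed and may say what happens to data after withdrawal. The finding is limited to the text available, and the fix must agree with those enclosures. They would not be expected to name an analysis method.

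*The size depends on chosen assumptions.* This stands. Bias in change and the false-positive rate fall sharply when the T1 score, rather than T1 change, drives loss. But the raw follow-up differences then grow, so the problem moves rather than disappears. Against the 12.8-point planning difference, 2.3 to 2.9 points is 18% to 23%.

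*The arms are alike.* Both do the same exercises on the same schedule, so similar loss is plausible, and similar loss gives about no bias under the null. A reader might take the 17.5% to 28.5% false-positive rates as the expected harm. They need patients doing badly to leave one arm and patients doing well to leave the other, which nothing in the documents predicts.

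*The mixed model is one option among several.* Also fair. Loss before T1 was not simulated; for those patients only T0 is available, and the model has little to work with.

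**Conclusion.** The gap is real and should be fixed. The documents leave the handling of leavers' completed data open, and the named test most likely turns the primary comparison into one of completers. That comparison is biased only if loss relates to outcome and differs by arm, in rate or in direction. With a marked imbalance (30% v 10%), bias is about 0.5 to 2.9 points in ODI change and 0.7 to 2.9 in raw follow-up scores, depending on what drives loss. With moderate imbalance it is smaller, and with equal loss in the same direction it is about nil under the null.

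All loss rates, directions and correlations are assumptions. The documents do not support a claim that bias will occur or that it will favour the video arm. Patients know whether they have the video or the brochure, but the text does not say whether they know which is experimental. Bias, not power, is the issue. Confidence is high on the ambiguity and its likely consequence; the size is illustrative.

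**What to change.** In Sections 7.2 and 8:

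- State that all randomised patients are analysed in the group assigned.
- State that abandonment ends participation, but data collected before it are kept unless the patient withdraws consent to their use, in agreement with the consent documents. Define *acquisition*.
- Replace repeated-measures ANOVA with a method that uses every available T0, T1 and T2 value, for example a linear mixed model (SPSS MIXED, as SPSS is already named) with group, time and group-by-time. Report the between-arm difference in ODI change at T1 and T2.
- Add one sensitivity analysis for outcome-related loss in which the assumption may differ by arm; its form is the statistician's choice.
- Report the number lost and the reasons, by arm.

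The cost is wording and a little more analysis of data already collected: no extra patients, visits or staff. The downside is that the mixed model removes the bias only if loss depends on observed data, which cannot be tested; hence the sensitivity analysis.
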